## **Protocol Title: Trial to Improve Multisensory Neural Processing, Language & Motor Outcomes in Preterm Infants**

---

starting at 32 0/7 weeks postmenstrual age (PMA). ERP testing will be performed prior to intervention and after intervention is complete., which occurs at 36 weeks PMA on average. ERP testing takes approximately 30 to 40 minutes. All infants will be seen at the NICU Follow-Up Program clinics at 3-4months PMA, 9-12 months PMA (Year 1) and 22-24 months PMA (Year 2), where neurodevelopmental outcomes will be assessed using standardized methods. If for any reason these standardized assessments are not able to be performed at the NICU Follow Up Clinic (e.g., parent request, infant not eligible to be seen in the NICU Follow Up Clinic), then the follow up visits will be conducted in the BBOP lab space with trained study personnel. Home visits may be provided on occasion, at the discretion of the Principal Investigator. If an in person visit is not able to be performed, we may do assessments virtually (e.g., zoom).

### **Study procedures**

For infants who meet inclusion criteria at 31 weeks, consent is obtained and parent's voice is recorded and parent-scented T-shirt may be collected when possible. Study staff may approach parents of eligible infants about the study and obtain consent slightly before the infant is 31 weeks, however, other study procedures will not start until the infant reaches 31 weeks. Infants are then randomized to the control or intervention group. If a patient is randomized to the control group, parents will be given the opportunity to consent to the secondary part of the study if they are interested. This part of the study is observational only and does not influence randomization. ERP testing is performed prior to the intervention. Infants assigned to the MS group receive the standardized MS intervention over 2 weeks, starting at 32 0/7 weeks PMA or at enrollment prior to 36 weeks. For both control and intervention groups, standard care includes skin-to-skin care on parent, when present, and playing of parents' voice non-contingent on infant suck. Parents may be asked to complete the Baby Care Questionnaire (BCQ) during infant's stay in the NICU or as soon as possible after discharge. Prior to the infant's discharge, a brief neurological examination (HNNE) and motor assessment (GMA) may be completed. ERP is repeated after intervention is completed, which occurs at 36 weeks PMA on average.

All infants are seen at the NICU Follow-Up Program clinics at 3-4, 9-12 (Year 1) and 22-26 months (Year 2). At the 3-4 month visit, study staff may obtain the Baby Care Questionnaire (BCQ), a brief neurological exam (HINE), and a brief motor assessment (GMA). At the Year 1 visit, study staff may obtain the BCQ, Infant Toddler Sensory Profile (ITSP), HINE, GMA, Bayley III, and the Parenting Styles and Dimensions Questionnaire (PSDQ). At Year 2, study staff may obtain the the Bayley III, HINE, BCQ, CBCL, PSDQ, and PLS-5.

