**Table 1**

| Construct   | Procedure(s)                     | Timing                              | Variable derived   | Variable type |
|--|---|--|---|----------------------|
| Multisensory response (Auditory-Tactile processing) | ERP to simultaneous puff + speech sound | Pre and post intervention (near discharge) | Pre-Post change in amplitude at frontal scalp locations in 176-377 ms time window                           | continuous           |
|  |   |  | IMP: Percentage of time spent in near-typical neural activation   | continuous           |
| Sensory reactivity and adaptation to environment    | ITSP                                    | 9-12 months                                | Behavioral neurological threshold score (typical or atypical)   | nominal              |
|  |   |  | Raw score in sensory processing domain  | continuous           |
| Language  | Bayley III                              | 22-26 months                               | Composite standard score
Scaled standard scores for expressive and receptive components                  | continuous           |
| Motor   | Bayley III                              | 22-26 months                               | Composite standard score
Scaled standard scores for fine and gross components                            | continuous           |
|  | Neurological Exam                       | 9-12 months
22-26 months                |   |                      |
| Tactile processing                                  | ERP to calibrated air puff              | Baseline/
After intervention            | Amplitude of response in 171-240 time window at central and frontal scalp locations                         | continuous           |
| Functional tactile connectivity                     | ERP to calibrated air puff              | Baseline/
After intervention            | Absolute clustering coefficient of alpha band coherence network   | continuous           |
| Speech Sound differentiation                        | ERP to 6 speech sounds                  | Baseline/
After intervention            | Difference in absolute amplitude between /du/ and /gu/ in frontal scalp locations in 250-350 ms time window | continuous           |

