#### **Study design and setting**

In order to test these aims, we are conducting an RCT of a multisensory (MS) intervention with 230 hospitalized preterm infants. Infants starting at 31 weeks will be randomized to either the control or intervention group. Both the control and intervention groups will receive standard care. Infants assigned to the MS group will also receive the MS intervention over two weeks,

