*Covariates:* Biological variables are factored into our research design as potential covariates. Several pretreatment covariates will be statistically controlled if needed. These variables will be quantified at the pretreatment period, as past research or theory suggests they may be associated with neurodevelopmental outcomes or sensory processing. If preliminary tests of between-group differences of these pretreatment variables and the pretreatment variables showing between-group differences are associated with putative mediators or neurodevelopmental outcomes, these will be statistical controlled. Their statistical interaction with treatment group must be tested as part of the process of determining whether they should be statistically controlled. Thus, the possibility that treatment varies as a function of these biological variables will also be explored. These include: gestational age at birth, sex, presence of severe white neural injury on neuroimaging (intraventricular hemorrhage grade III or IV, periventricular leukomalacia, cerebellar hemorrhage, ischemic or thrombotic injury), presence of systemic inflammatory conditions (history of necrotizing enterocolitis Bells Stage

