*MS intervention protocol:* The MS intervention will be carried out in addition to standard care and will include two components: holding and light pressure containment of the infant against the cotton T-shirt covered chest of the therapist for tactile and non-specific auditory stimulation **simultaneous with** playing of mother's voice contingent on infant pacifier sucking for during a study session of no more than 15 minutes duration. No more than one study session will be completed per care period for each subject. Additionally, when possible, a 100% cotton T-shirt square scented with parent's skin may be placed within 2 cm of infant's face on the therapists' chest, to provide olfactory stimulation without risk of suffocation. The 12-23 intervention sessions will be dispersed across 2-3 weeks.

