### **Assessment Methods**

Our outcomes (or constructs) of interest are listed in Table 1. These constructs are quantifiable using well validated tests and measures. Our primary outcome is multisensory response and our secondary outcome is neurodevelopmental outcomes, including sensory adaptation, motor, language, tactile processing, and speech sound differentiation.

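### The second ERP is dated by finishing an intervention that controls never receive, with no common window, so age at the primary outcome test can differ by arm

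*Combined protocol and SAP*

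**What the plan says.** Assessment Methods states "Our primary outcome is multisensory response". Table 1 derives two variables from it: pre-post amplitude change at frontal sites, and the index of multisensory processing (IMP), the share of time in near-typical activation.

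The second ERP is dated in three places.

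- Study design and setting: "ERP testing will be performed prior to intervention and after intervention is complete., which occurs at 36 weeks PMA on average".
- Study procedures: "ERP is repeated after intervention is completed, which occurs at 36 weeks PMA on average".
- Table 1, multisensory row: "Pre and post intervention (near discharge" (closing bracket omitted here).

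Only one arm has an intervention to complete: "Infants assigned to the MS group will also receive the MS intervention over two weeks" (Study design and setting). It begins "starting at 32 0/7 weeks PMA or at enrollment prior to 36 weeks" (Study procedures). Its length is two weeks in those two sections, but Multisensory Intervention says "The 12-23 intervention sessions will be dispersed across 2-3 weeks". The Study Summary places the NICU intervention between 32 and 36 weeks PMA.

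The Covariates paragraph under Randomization begins its list with "gestational age at birth, sex, presence of severe white neural injury on neuroimaging" and continues with inflammatory conditions, caffeine, skin-to-skin time and General Movements status. These enter only if they differ between groups and relate to a mediator or outcome. Power/Sample Size adds that pretreatment ERP is always controlled. Age at either ERP and the time between ERPs are not named.

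**The concern.** An infant's ERP may change with age over these weeks whether or not the infant is treated. A comparison at the second ERP is fair only if both arms are tested at the same ages, or at the same interval from baseline. Randomisation balances age at entry. It does not balance the date of a later test that is set by an event in one arm only.

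Both primary variables are exposed. The IMP scores likeness to a full-term rather than a preterm template, so age at test is a rival explanation for a more typical result. The amplitude variable is not scored against a template, but as a change score it depends on the interval between tests. The same measure is the mediator in Aim 2, so a timing difference would also enter the path from treatment to mediator.

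**Working it through.** **1. Is there a control-arm rule?** Read together, the three timing statements give one event that only the MS arm has (completion), one that both arms have (discharge), and an average (36 weeks PMA). None states a window, a fixed interval or a control date. The only explicit time limit for an ERP is the 24-hour retest when data are insufficient (Randomization, Total attrition).

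**2. How far could completion dates spread?**

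- Earliest: 32 0/7 + 2 weeks = 34 0/7 weeks.
- Latest: a start just before 36 0/7 + 3 weeks = just under 39 0/7 weeks.

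This is a worst case of about five weeks. If the Study Summary's 32 to 36 weeks caps completion, the spread is 34 to 36 weeks. A start at 32 0/7 with 2 to 3 weeks of sessions ends at 34 to 35 weeks, so a 36-week average implies later starts or a gap before testing. The sections do not settle which.

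**3. Do the planned covariates remove a timing difference?** Pretreatment ERP captures status at baseline, not maturation afterwards. Gestational age at birth does not fix age at the second test, and it enters only conditionally. Neither corrects for unequal timing.

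**4. The plan's own power figures.** Inputs from Statistical Analysis are a one-tailed test, N = 180, and g = 0.74 or 0.35. Alpha is not stated; I assume 0.05. With equal arms, power = Φ(g√(N/4) − 1.645), and √(180/4) = 6.708.

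- g = 0.74: Φ(4.964 − 1.645) = 99.95%. The stated figure of over 99% is reproduced.
- g = 0.35: Φ(2.348 − 1.645) = 75.9%. The stated figure of over 80% is not reproduced by an unadjusted test. It is reached at N = 207 (80.9%), or at N = 180 if baseline ERP correlates about 0.33 or more with the outcome, a value the plan does not give.

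Separately, 10% attrition from 230 leaves 207; 180 is 90% of the former 200. I use 180 below because it is the plan's figure.

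**5. What a timing gap would do.** The documents give neither a maturation rate nor a gap. I assume 0.1 to 0.3 SD per week, in the direction counted as benefit, and gaps of 0, half a week and one week.

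- Bias b = rate × gap.
- False-positive rate if the MS arm is tested later = Φ(6.708b − 1.645).
- Power for g = 0.35 if the MS arm is tested earlier = Φ(6.708(0.35 − b) − 1.645).

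| Gap (weeks) | Rate (SD/week) | Bias (SD) | False-positive rate, MS later | Power, MS earlier |
|---|---|---|---|---|
| 0 | any | 0 | 5% | 75.9% |
| 0.5 | 0.1 | 0.05 | 9.5% | 64.3% |
| 0.5 | 0.3 | 0.15 | 26.2% | 38.1% |
| 1 | 0.1 | 0.10 | 16.5% | 51.3% |
| 1 | 0.2 | 0.20 | 38.1% | 26.2% |
| 1 | 0.3 | 0.30 | 64.3% | 9.5% |

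A one-week gap gives a bias of 0.10/0.35 = 29% to 0.30/0.35 = 86% of the plan's minimum effect. At N = 207 the one-week false-positive rates are 17.7%, 41.8% and 69.6%.

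**The case against.** The strongest reply is that completion is not the only anchor. Table 1 says near discharge, and the aims place multisensory processing at discharge. Both arms have a discharge, so staff may already test controls on a comparable schedule. This stands as far as it goes: the defect is a missing common rule and window, not proof that controls are tested at other ages.

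Other parts of the reply also stand. The 39-week bound joins the latest start to the longest duration, is not actually reached, and may be excluded by the Study Summary. Only the IMP is scored against a full-term template. The rate and the gap are assumptions. Age at baseline ERP should be balanced by randomisation, so adjusting for it adds precision but does not remove a difference in second-test timing. The covariate list is introduced as inclusive, so age at test is not ruled out, although nothing commits the analysis to it.

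A reader might infer that the design favours treatment because treated infants will be tested older. The documents do not support that. They give no PMA by arm and no maturation rate, and controls tested close to discharge could equally be the older group.

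Finally, Inclusion and Exclusion Criteria reports Covid losses and the rise from 200 to 230, which suggests that the trial is under way. A rule that tested treated infants before their last session would also conflict with Aim 1, which places the ERP comparison after the intervention has ended. Both points limit the remedy but do not answer the concern.

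**Conclusion.** The point holds as an unguarded risk. The test that carries the primary outcome is dated by an event in one arm, the shared anchors have no window, and no planned covariate corrects for age at the second test or for the interval between tests.

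Size and direction are unknown. Equal timing gives zero bias. A one-week gap at an assumed 0.1 to 0.3 SD per week gives 0.1 to 0.3 SD, and a one-tailed false-positive rate of about 16% to 64% at N = 180 if the MS arm is tested later. If it is tested earlier, power for g = 0.35 falls from 76% to between 51% and 10%. These figures show sensitivity under stated assumptions and do not estimate what the trial will do. That the primary result is biased, or that a positive finding would be a maturation artefact, does not follow from the documents.

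**What to change.** 1. Date the second ERP by one rule in both arms, with a stated window. Options are a control date fixed at randomisation from the planned intervention length, or a common interval from baseline ERP. Set the window late enough for sessions to finish, so that Aim 1's comparison still follows the intervention. Apply the rule to infants not yet tested, and say what happens when an infant goes home before the date.
2. Add PMA at baseline ERP (or at enrolment) as a fixed covariate in every ERP model. The purpose is precision.
3. Report PMA at the second ERP and the interval between ERPs by arm for all infants, including those already tested. Adjust for them only in a prespecified sensitivity analysis, because both arise after randomisation.
4. Reconcile the statements on when the intervention starts, how long it lasts and when it ends (Study Summary, Study design and setting, Study procedures, Multisensory Intervention).

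The cost is protocol and analysis wording, plus variables derived from birth and test dates. The drawbacks are two timing schedules in the ERP data if the trial is already under way, and slightly less flexible test scheduling.

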## **Protocol Title: Trial to Improve Multisensory Neural Processing, Language & Motor Outcomes in Preterm Infants**

---

If for any reason these standardized assessments are not able to be performed at the NICU Follow Up Clinic (e.g., parent request, infant not eligible to be seen in the NICU Follow Up Clinic), then the follow up visits will be conducted in the BBOP lab space with trained study personnel. Home visits may be provided on occasion, at the discretion of the Principal Investigator. If an in person visit is not able to be performed, we may do assessments virtually (e.g., zoom). Individual assessment results may be shared with the families at their request and after the scoring has been completed. In addition, if a participant is seen outside of the NICU Follow Up clinic for their study follow up assessments, we may also share results with a participant's primary care provider or the NICU Follow up Clinic (with the parent's permission) with any concerns that were identified.

### **Inclusion and Exclusion Criteria**

The study population was originally comprised of 200 preterm infants. Due to Covid 19 losses to follow up, this number has been revised to 230 preterm infants. We anticipate the distribution to be 45% male and 55% female, as females have a small survival advantage after extreme prematurity. All races and ethnicities will be included, with an expected skew towards slightly more black children due to disproportionate effects of prematurity on race.

Inclusion criteria includes PMA 32 0/7 weeks gestation-36 0/7 weeks gestation. Exclusion criteria will be ventilation using an endotracheal tube, major congenital malformations, family history of genetic hearing loss, and use of sedatives or seizure medications. These medications may mask sensory processing as assessed by ERPs.

### **Randomization**

Random assignment to groups will be carried out using unified reproducible methods (i.e. saved random number seeds) provided by our Biostatistics core. We will try to conceal allocation from all study personnel who could influence scores. Except for parent reports, examiners will be blind to treatment assignment. We will obtain recorded parent's voice from both groups with the intent of masking parents to assignment. Although we cannot fully mask parents to group allocation, as bedside nurses communicate regularly with them, we will address the potential effect on the parent questionnaire at one-year by deemphasizing the sensory nature of the outcomes to both groups, and instead focusing on the proven positive links between parental involvement and improved intersubjectivity.

## **Protocol Title: Trial to Improve Multisensory Neural Processing, Language & Motor Outcomes in Preterm Infants**

---

*In addition to randomization, we have addressed the problems of RCT design as follows:*

*Adherence to treatment protocol:* A highly manualized treatment for the MS treatment while monitored control treatments will be used by hospital staff during NICU hospitalization. These measures should help ensure uniform, high-quality implementation of the MS treatment. Sufficiently and randomly sampled fidelity of treatment (FOT) measures will be collected. Two of the first twelve MS sessions will be video recorded for study team review to ensure FOT. Treatment is provided in the NICU by experienced staff therapists.

*Total attrition:* Total attrition is expected to be less than 10% We have experienced <5% data loss due to non-compliance with electrode placement in our prior studies. Should motion artifact occur, we will retest patients with insufficient data within 24 hours. For the Bayley, should children prove unable to complete follow-up testing during scheduled visits, they will be rescheduled within one week of the scheduled visit. Testers are trained to perform the Bayley III in the home environment, if necessary, The ITSP can be performed over the phone or through the mail if necessary and will be performed within one week of a missed visit.

The BCQ and PSDQ may be completed by the parent in writing or via phone. Analysis will follow an intent-to-treat protocol. As such, all randomized participants will be analyzed and missing data will be handled using multiple imputation.

*Differential attrition:* Differential attrition is unlikely because children must be in the NICU during the treatment phase due to health concerns. There are no non-NICU treatments during the treatment phase. Thus, compensatory responses due to parental displeasure of group assignment is unlikely.

*Covariates:* Biological variables are factored into our research design as potential covariates. Several pretreatment covariates will be statistically controlled if needed. These variables will be quantified at the pretreatment period, as past research or theory suggests they may be associated with neurodevelopmental outcomes or sensory processing. If preliminary tests of between-group differences of these pretreatment variables and the pretreatment variables showing between-group differences are associated with putative mediators or neurodevelopmental outcomes, these will be statistical controlled. Their statistical interaction with treatment group must be tested as part of the process of determining whether they should be statistically controlled. Thus, the possibility that treatment varies as a function of these biological variables will also be explored. These include: gestational age at birth, sex, presence of severe white neural injury on neuroimaging (intraventricular hemorrhage grade III or IV, periventricular leukomalacia, cerebellar hemorrhage, ischemic or thrombotic injury), presence of systemic inflammatory conditions (history of necrotizing enterocolitis Bells Stage

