## **Protocol Title: Trial to Improve Multisensory Neural Processing, Language & Motor Outcomes in Preterm Infants**

---

IIA or above, culture documented sepsis or meningitis, moderate or severe bronchopulmonary dysplasia per modified Shennan definition), cumulative caffeine exposure post intervention, total parental skin-to-skin time during the study period and pretreatment status on the General Movements Assessment (GMA).

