### **Analysis Plan**

#### **Power/Sample Size**

A total sample size of 230 (115 in each group) will be recruited. Although attrition in past similar work has been much lower, we estimate power under an assumption of 10% attrition (i.e., 180). Because pilot studies afford effect size estimates with wide confidence intervals due to small sample sizes, power analysis results were conducted for the effect size available from pilot data and lowest effect size that the after-attrition sample size affords. Feasibility of the expected effect size is then evaluated. Power analyses are based on primary variables (multi- and uni- sensory processing). If between-group differences occur on the putative covariates (i.e., pretreatment variables related to the outcomes) and they are associated with putative mediators or outcomes, the pretreatment variables will be statistically controlled after ensuring that the homogeneity of slopes assumption has been met. Pretreatment ERP variables will be statistically controlled regardless of the effect size of between-group differences to improve effect size estimates. Missing data will be handled using multiple imputation.

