## Protocol Title: Trial to Improve Multisensory Neural Processing, Language & Motor Outcomes in Preterm Infants

---

When the dependent variable is continuous, we will use ANOVAs when controlling for pretreatment variables and independent sample t-tests when there is no need for a covariate. When testing the nominal form of the sensory reactivity and adaptation outcome, we will use logistic regression.

*Statistical power:* Using PASS software, the estimated power using a 1-tailed test for an effect size based on the pilot data (Hedges  $g = .74$ ) with a sample size of 180 is over 99%. Even if the actual effect size is  $g = .35$ , we will have over 80% power to detect the effect under the proposed conditions. Detecting the required minimum effect size is probably for a number of reasons.

First, the expected effect size for the proposed treatment on multisensory processing should be larger than that derived from the pilot because the treatment used in the pilot

(i.e., skin-to-skin contact *without* the suck-contingent presentation of parent's voice) and theory strongly suggests the multisensory treatment will produce a larger effect than a unisensory treatment. Secondly, a medium main effect size of the proposed treatment on neurodevelopmental outcomes is expected because multisensory processing is moderately to strongly associated with later neurodevelopmental outcomes.

*Our second aim is to test the role of multisensory responses at discharge in mediating intervention effects on later sensory adaptation, and motor and language outcomes.*

Mediation models are presented in Figure 3. The indirect effect (the product of the a path coefficient \* the b path coefficient) will be tested for significance using the bias-corrected bootstrap method. The a path is the main effect of treatment on the ERP measure of multisensory processing. The b path is the association of the ERP measure of multisensory processing with the outcome controlling for the treatment group.

[figure not shown]

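### Adjustment for the listed covariates hangs on imbalance, association and slopes tests, which gives up nearly all the precision they offer, and two of them are measured after randomisation

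*Combined protocol and SAP*

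**What the plan says.** The rule is spread over three places.

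- **Randomization, Covariates paragraph.** "Several pretreatment covariates will be statistically controlled if needed". The condition begins "If preliminary tests of between-group differences of these pretreatment variables" and goes on to require that the imbalanced variables "are associated with putative mediators or neurodevelopmental outcomes, these will be statistical controlled". A further step follows: "Their statistical interaction with treatment group must be tested as part of the process of determining whether they should be statistically controlled". The variables are said to be measured in the pretreatment period. Seven are listed: gestational age at birth, sex, severe brain injury on imaging, systemic inflammatory conditions, "cumulative caffeine exposure post intervention, total parental skin-to-skin time during the study period", and pretreatment General Movements Assessment (GMA).
- **Power/Sample Size.** This repeats the imbalance and association conditions and says that "the pretreatment variables will be statistically controlled after ensuring that the homogeneity of slopes assumption has been met". It then makes one exception: pretreatment ERP variables are controlled whatever the group difference.
- **Statistical Analysis, Aim 1.** Continuous outcomes get an ANOVA when a pretreatment variable is controlled and "independent sample t-tests when there is no need for a covariate". The nominal ITSP outcome gets logistic regression.

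None of these places gives a level for the preliminary tests, a fixed covariate set, or a rule for what happens when slopes are not homogeneous.

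**The concern.** In a randomised trial, a baseline difference between arms is chance. A test for imbalance therefore says nothing about whether a covariate is worth having in the model. What matters is how strongly it predicts the outcome. The rule uses prognostic strength only as a second hurdle, after imbalance, so a strongly prognostic variable that happens to be balanced is left out. The Aim 1 model for these covariates is also not known until the data have been examined, with the test levels left to the analyst.

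The two variables measured after randomisation raise a different problem. If assignment affects skin-to-skin time or caffeine exposure, the arms will differ on it, and that difference is what the first test looks for. The rule would then tend to admit the variable in exactly the case where adjusting for it can take out part of the treatment effect. The Randomization section accepts that parents cannot be fully masked, so an effect of assignment on parental skin-to-skin time cannot be ruled out.

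**Working it through.** **Inputs.** From Power/Sample Size and the Aim 1 power paragraph: 180 analysed (taken as 90 per arm), one-tailed test, g = 0.74 and g = 0.35. Assumed, because the documents give neither: alpha 0.05, and the share of outcome variance (R²) explained by the covariates.

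**1. The plan's own figures.** For an unadjusted comparison, power = Φ(g·√(n/2) − 1.645) with n = 90.

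- g = 0.74: 0.74 × √45 = 4.964, and Φ(4.964 − 1.645) is above 99.9%. The stated figure of over 99% reproduces.
- g = 0.35: 0.35 × √45 = 2.348, and Φ(0.703) = 75.9% (75.6% with the noncentral t). The stated figure of over 80% does not reproduce for a t-test on 180. It is reached with 103 per arm (80.7%), close to 230 × 0.9 = 207. The analysed number is a separate matter, but it means there is no slack to give away here.

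**2. Fixed ANCOVA, same basis.** Replace g by g/√(1 − R²).

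| R² (assumed) | g·√45/√(1 − R²) | Power |
|---|---|---|
| 0 | 2.348 | 75.9% |
| 0.10 | 2.475 | 79.7% |
| 0.20 | 2.625 | 83.7% |
| 0.30 | 2.806 | 87.7% |

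**3. The rule as written, one covariate.** Simulation with one normal covariate, 90 per arm and 100,000 trials per scenario. Imbalance, association and slopes tests were each two-sided at an assumed 0.05. ANCOVA was used only if all three were passed, otherwise the t-test. A failed slopes test was taken to mean no adjustment, which is a modelling choice because the plan is silent.

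| Covariate–outcome correlation | Gate opens | t-test | Rule as written | Fixed ANCOVA | One-sided type I error of the rule |
|---|---|---|---|---|---|
| 0.30 | 4.67% | 75.69% | 76.00% | 78.89% | 4.76% |
| 0.42 | 4.79% | 75.54% | 76.26% | 82.29% | 4.57% |
| 0.55 | 4.84% | 75.64% | 76.86% | 87.45% | 4.45% |

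The share of the available gain that the rule keeps is (rule − t-test)/(ANCOVA − t-test). That is 0.31/3.20, 0.72/6.75 and 1.22/11.81, or about 10% each time. The correlation of 0.42 borrows the size of the Bayley correlation quoted under Aim 2. It is an illustration, not an estimate for these covariates.

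**4. Five covariates.** With five independent baseline covariates, the chance that at least one is flagged as imbalanced is 1 − 0.95⁵ = 22.6%. A simulation of the full rule with five covariates (103 per arm, two-sided 0.05, g = 0.35, 6,000 trials per scenario) gave the following power. Its basis differs from steps 1 to 3, so only the comparison within rows matters.

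| Total R² (assumed) | t-test | Rule as written | Fixed ANCOVA |
|---|---|---|---|
| 0.10 | 71% | 70% | 74% |
| 0.20 | 71% | 71% | 79% |
| 0.30 | 71% | 72% | 84% |

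The model changes more often than with one covariate, but power still stays close to the t-test. Type I error was 4.4% to 4.7%.

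**5. Timing.** The Covariates paragraph says that its variables are measured before treatment. By their own descriptions, caffeine exposure after the intervention and skin-to-skin time over the study period cannot be. GMA is called pretreatment there, but Study procedures mentions it only as an optional assessment before discharge and at follow-up visits.

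**The case against.** The best defence is that the most important covariate escapes the gate. The primary outcome is the multisensory ERP response, and pretreatment ERP is always controlled. This stands, and it confines the point to the seven listed covariates. The loss matters most for outcomes with no baseline value of their own.

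The documents do not support several stronger readings that a reader might infer.

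- *Bayley outcomes default to an unadjusted t-test.* The sentence on pretreatment ERP is not limited to ERP outcomes. If it applies to all of them, the Bayley and ITSP models are adjusted for it. The fault is that the plan does not say.
- *Imbalance alone triggers adjustment.* Association with a mediator or outcome is also required.
- *A failed slopes test discards the covariate.* The condition is "statistically controlled after ensuring that the homogeneity of slopes assumption has been met", but no consequence of failure is given, and the Covariates paragraph says that variation in the treatment effect will be explored.
- *The p-values are invalid.* In these simulations the rule is slightly conservative. What is shown is lost power and analyst discretion.
- *There is a 30% chance that randomisation alone flags a covariate.* That is 1 − 0.95⁷ = 30.2%. It assumes a 0.05 level and independence, and it counts the two variables measured after randomisation, whose group difference need not be chance. It is also the chance of a first-stage flag, not of a changed model.

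It is also fair to say that the documents give no R² for these covariates, and that the ANCOVA formula does not carry over to the nominal ITSP outcome.

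**Conclusion.** The point holds for the listed covariates. The rule makes their use depend on the data and keeps about a tenth of the power gain from adjustment. On the plan's basis (g = 0.35, 180 analysed, one-tailed) that means about 76% power instead of 79.7% to 87.7%. This rests on an assumed alpha of 0.05, preliminary tests at an assumed 0.05, independent normal covariates where five were simulated, and an assumed R² of 0.10 to 0.30. If the covariates explain little, little is lost. Type I error is not inflated. Bayley and ITSP are most exposed, because it is unclear whether pretreatment ERP enters their models.

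Listing two variables measured after randomisation as pretreatment is an internal contradiction that needs no assumption to establish. Whether adjusting for them would bias the effect depends on whether assignment changes them, which the documents do not settle.

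**What to change.** - Prespecify one model per outcome: ANCOVA for continuous outcomes and logistic regression for nominal ITSP. Include treatment and a fixed set of baseline covariates: gestational age at birth, sex, severe brain injury and inflammatory conditions, the last two as present before randomisation.
- Add pretreatment ERP for ERP outcomes, and state whether it also enters the Bayley and ITSP models.
- Drop the imbalance and slopes gates. Report treatment-by-covariate interactions as exploratory.
- Remove post-intervention caffeine exposure and skin-to-skin time during the study from the Aim 1 adjustment set.
- Reconcile the Covariates paragraph with Study procedures on when GMA is done, and include it only if it is actually obtained before treatment.

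The cost is SAP wording and a few degrees of freedom. No new data are needed for the core set, provided that the timing of brain injury and inflammatory conditions can be established from the records.
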